Interventions	Continue Group Patients in the continue group will continue with their ACE-I and/or ARB 72 hours prior to the day of surgery and continue for at least 48 hours after surgery. Stop Group Patients in the stop group will stop their ACE-I and/or ARB [according to half-life of each individual drug] prior to the day of surgery through to at least 48 hours after surgery.

Primary outcome measure	The primary outcome is myocardial injury, a binary variable based on plasma high sensitivity Troponin-T measured in blood samples collected immediately before the induction of anaesthesia, and then postoperative day 1± 6 hours and day 2±6 hours. The primary outcome is met under the following conditions: • Troponin-T ≥15 ng/L within 48 hours after surgery with a pre-operative value <15 ng/L OR • Troponin-T increase ≥5 ng/L within 48 hours after surgery with a pre-operative value ≥15ng/L

3. Outcome measures

Primary outcome measure

The primary outcome is myocardial injury, a binary variable based on plasma high sensitivity Troponin-T) measured in blood samples collected immediately before the induction of anaesthesia, and then postoperative day 1 ± 6 hours and day 2 ± 6 hours after surgery. The primary outcome is met under the following conditions:

- Troponin-T ≥15 ng/L within 48 hours after surgery with a pre-operative value <15 ng/L OR
- Troponin-T increase ≥5 ng/L within 48 hours after surgery with a pre-operative value ≥15ng/L

Secondary outcome measures

- Peak level of Troponin-T measured within 48 hours of surgery. Peak Troponin-T level (ng/L) will be calculated as the highest Troponin-T from the blood samples collected at 24 hours and 48 hours after surgery.
- Infection within 30 days of surgery
- Myocardial infarction within 30 days of surgery
- Acute heart failure within 30 days of surgery
- Stroke within 30 days of surgery
- Death within 30 days of surgery

Full definitions of secondary outcome measures can be found in the SPACE protocol.

4. Sample size and randomisation

Sample size calculation

Assuming incidence of postoperative myocardial injury of 50% in patients undergoing major surgery in the cessation group, a sample size of 248 patients will provide 90% power to detect as statistically significant (p<0.05) an 20% absolute risk reduction to 30% [1, 2]. Allowing for 5% withdrawal/loss to follow up, we will aim to recruit a total of 260 patients.

Randomisation procedure

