The amount of missing primary outcome data is anticipated to be minimal but will be accounted for in a sensitivity analysis if missing data is greater than 5%. The primary analysis will be repeated once assuming that all patients in the continue group with missing outcomes did not experience myocardial injury, and all patients in the stop group with missing outcomes experienced myocardial injury. The analysis will then be repeated again with the opposite assumptions. This will then give the absolute range of how much the results could change if the data were complete. This will also assess the robustness of our analysis of the primary outcome under the assumption that data is missing-not-at-random (MNAR).

6. Other analyses, data summaries and graphs

Clinical management

Clinical management for the continue group and stop group will be summarised but not subjected to statistical testing. Numbers (%) and means (SD) or medians (IQR) will be provided separately for each group. The continue and stop groups will be compared for the following clinical management characteristics:

- Surgical technique
- Anaesthetic technique
- Planned and actual level of care on the first night after surgery
- Blood pressure during surgery
- Intravenous fluids during surgery

Process measures

Summary measures will be presented separately for each treatment group. All patients with recorded data will be included in the summary. Formal statistical analysis will not be performed. Duration of hospital stay after surgery (days) and total duration of critical care stay within 30 days of surgery (days) will be summarised using mean (SD) and median (IQR). Re-admission to hospital within 30 days of surgery will be presented as number (%).

Safety analyses

Adverse events and serious adverse events will be presented as a number (%) by treatment group. All patients with a recorded outcome will be included in the summary. In addition to this, 'other' adverse events will be reported separately if prevalence is more than 5% across all participants in the trial.

Protocol deviations

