Appendix 1: Derived outcomes and variables

Variables

Revised cardiac risk index for pre-operative risk (RCRI)

RCRI is the sum of the following 6 components of the score:

- Elevated-risk surgery (Intraperitoneal; intrathoracic; suprainguinal vascular): 0=No; 1=Yes
- Ischaemic heart disease: 0=No: 1=Yes
- Heart failure: 0=No; 1=Yes
- Cerebrovascular disease (Prior TIA or stroke): 0=No; 1=Yes
- Pre-operative treatment with insulin (diabetes mellitus): 0=No; 1=Yes
- Pre-operative creatinine >2 mg/dL / 176.8 μmol/L: 0=No; 1=Yes

RCRI Score will range from 0-6. The total score will be set to missing if any items are missing.

Primary outcome

Myocardial injury within 48 hours of surgery

- Equal to 1 (Event) if:
 - Troponin-T ≥15 ng/L within 48 hours after surgery with a pre-operative value <15 ng/L or
 - Troponin-T increase ≥5 ng/L within 48 hours after surgery with a pre-operative value ≥15ng/L
- Equal to 0 (No Event) if:
 - o If the above definition of an 'event' is not satisfied and data collected on T-troponin pre-operative and post-operative day 1 or 2 is complete
- Equal to missing if:
 - o Data is missing for T-troponin pre-operative and post-operative day 1 & 2
 - Data is missing for T-troponin pre-operative and T-troponin post-operative day 1 & 2 is complete

Secondary outcomes

Peak level of Troponin-T measured within 48 hours of surgery

This is defined as the highest troponin-t value measured within 48 hours of surgery which is collected on post-op day 1 or day 2. If only one troponin-T value is available on post-op day 1 or day 2 then this will be used as the peak. If troponin-T data is missing for both post-operative day 1 & 2, then the outcome will be set to missing.

Infection within 30 days of surgery

This is defined as one or more of the following infections (more detail on the definition of each type of infection is available in the SPACE protocol):

- Superficial surgical site infection
- Deep surgical site infection
- Organ space surgical site infection
- Urinary tract infection
- Infection, source uncertain
- Laboratory confirmed blood stream infection

Equal to 1 if:

 At least one of the components of infection is listed as occurring (i.e. listed under Clavien-Dindo grade I-V)

Equal to 0 if:

• All of the components of postoperative infection are "None"

Missing if:

- All components are missing
- OR one or more of the components of postoperative infection is missing and all other components are "None"

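### The extreme-case sensitivity analysis is not the absolute range it claims: one-sample negatives are never varied, and some patients coded missing are given an impossible event

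*SAP*

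**What the plan says.** Section 5, Sensitivity analysis, states that missing primary outcome data "will be accounted for in a sensitivity analysis if missing data is greater than 5" per cent. In one run, patients with missing outcomes in the continue group are taken as free of injury and "all patients in the stop group with missing outcomes experienced myocardial injury". In the second run the assumptions are swapped. Of the two together the SAP says: "This will then give the absolute range of how much the results could change if the data were complete".

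Who counts as missing is fixed in Appendix 1, Primary outcome. Section 3 schedules a pre-operative sample, "then postoperative day 1 ± 6 hours and day 2 ± 6 hours after surgery". A qualifying value at either post-operative sample makes an event; for example, the first condition is "Troponin-T ≥15 ng/L within 48 hours after surgery with a pre-operative value <15 ng/L". The second condition is a rise of at least 5 ng/L from a pre-operative value of 15 ng/L or more. A patient is a non-event if the event definition "is not satisfied and data collected on T-troponin pre-operative and post-operative day 1 or 2 is complete". The outcome is missing if all three values are absent, or under this rule: "Data is missing for T-troponin pre-operative and T-troponin post-operative day 1 & 2 is complete".

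**The concern.** The event rule is of the either-sample kind, so one qualifying sample settles an event but one negative sample does not settle a non-event. The non-event rule nevertheless accepts a single negative sample. Patients coded this way have incomplete data by any ordinary reading, yet the sensitivity analysis leaves them at 0 in both extremes and omits them from the percentage that decides whether it is run.

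The missing rule has the reverse fault for one group. It treats as unknown some patients whose outcome is already settled by their two post-operative values.

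This is the only planned check on missing primary outcome data. A reader told that the two results bracket everything complete data could show would place more trust in the bracket than the coding justifies.

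**Working it through.** **Step 1. Patterns set against the rules in Appendix 1**

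| Pre-operative | Post-operative day 1 and day 2 | Coding | Could complete data make it an event? |
|---|---|---|---|
| present | one qualifying, other absent | event | already settled as an event |
| present | one negative, other absent | non-event | yes |
| absent | both present, both below 15 ng/L | missing | no |
| absent | both present, at least one 15 ng/L or more | missing | yes |
| absent | both absent | missing | yes |
| present | both absent | not listed | yes |
| absent | only one present | not listed | yes |

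The second row is fixed at 0 although it is open. The third row is varied although it is closed: if the pre-operative value was below 15, an event needs a later value of 15 or more; if it was 15 or more, an event needs a later value of at least 20. Two values below 15 meet neither.

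**Step 2. Inputs**

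- 50% (stop) v 30% (continue), 248 patients, 90% power, 260 after loss: Section 4. Reproduced with the pooled-variance formula, two-sided 5%, no continuity correction: (1.960 × √0.48 + 1.282 × √0.46)² / 0.20² = 124 per arm, so 248. For loss, 248 × 1.05 = 260.4 and 248 / 0.95 = 261.05, so 260 is close enough.
- 260 at 1:1 gives 130 per arm.
- Coded missing, 7 per arm: an assumption, just over the trigger (14/260 = 5.4%). This leaves 123 per arm, with 62 events (stop) and 37 (continue), a risk difference of -20.3 points.
- One-sample negatives, k per arm: not given in the SAP. Assumed 3, 6 or 13 (about 2%, 5% and 10% of an arm).

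The SAP states no number for the range itself, so there is none to reproduce.

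**Step 3. Bounds on the risk difference** (continue minus stop, unadjusted)

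- Most favourable to continuing: [37 − (62 + 7 + k)] / 130 = −(32 + k)/130
- Least favourable: [(37 + 7 + k) − 62] / 130 = −(18 − k)/130

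Each unit of k moves each bound outwards by 1/130 = 0.77 points.

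| k per arm | Range (points) | Wald 95% CI at the least favourable bound |
|---|---|---|
| 0 (as planned) | -24.6 to -13.8 | -25.7 to -2.0 |
| 3 | -26.9 to -11.5 | -23.5 to +0.4 |
| 6 | -29.2 to -9.2 | -21.2 to +2.8 |
| 13 | -34.6 to -3.8 | -15.9 to +8.3 |

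**Step 4. Impossible events.** If m of the 7 per arm have no pre-operative value and both post-operative values below 15 ng/L, they belong at 0 in both runs. The bounds become −(32 + k − m)/130 and −(18 − k + m)/130, so each such patient per arm pulls each bound in by the same 0.77 points. The net error is (k − m)/130.

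**Step 5. Trigger.** With 4 coded missing per arm, 8/260 = 3.1% and nothing is run. If 6 per arm are also one-sample negatives, 20/260 = 7.7% have an open outcome. With 63 and 38 observed events, the range is −(63 + 4 + 6 − 38)/130 = -26.9 to −(63 − 38 − 4 − 6)/130 = -11.5. With none coded missing and 13 one-sample negatives per arm (65 and 39 events), it is −(78 − 39)/130 = -30.0 to −(65 − 52)/130 = -10.0, again with no analysis run.

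**The case against.** The best defence is that the rule is explicit and consistent. Section 5, General analysis principles, sends the reader to Appendix 1 for what counts as a recorded outcome, the non-event rule accepts either sample, and the peak-troponin rule also accepts a single value. For the outcome so defined, the two runs do vary everyone coded missing. The SAP also expects little missing data, and if no patient has one negative sample with the other absent, the narrowing disappears. All of this stands. It does not rescue the claim, which is about complete data and not about the outcome as coded.

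Four stronger readings are tempting but unsupported.

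- **That the primary estimate is materially biased.** Suppose 10% in each arm lack one sample and 15% of injuries show only on the missed one. The observed rates are then 50% × 0.985 = 49.25% and 30% × 0.985 = 29.55%, a difference of 19.7 instead of 20.0. If only one arm lacked samples, it would be 19.25 or 20.45. The shift is below 1 point.
- **That one-sample patients are the commonest partial pattern, or differ by arm through earlier discharge.** Nothing in the SAP says so.
- **That the 5% trigger can hide a reversed conclusion.** At exactly 13/260 missing, 58/124 v 42/123 (p = 0.043) has extremes of 16.9 points (p = 0.005) and 6.9 points (p = 0.26), and neither is run. Significance is lost in the second, but the direction holds, and the counts are chosen to be borderline. At the design effect (62/124 v 37/123) the adverse extreme is 62/130 v 44/130, 13.8 points, p = 0.023. Whether to have a threshold is a matter of judgement.
- **That the two unlisted patterns leave the outcome undefined.** They meet neither the event nor the non-event rule, and any analyst would code them missing. This is a drafting gap.

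**Conclusion.** The statement that the two runs give the absolute range under complete data is wrong as written. The range can be too narrow, through one-sample negatives fixed at 0, and too wide, through settled non-events treated as missing. The first group is also left out of the trigger count.

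The size depends on two counts that the SAP does not give. The net error is 0.77 points per bound for each patient per arm by which one-sample negatives exceed impossible events. The worked ranges assume 130 per arm, equal numbers in both arms, rates near the design values and no adjustment. The planned model is an adjusted mixed-effect logistic regression, so its odds-ratio limits will take other values but shift in the same directions.

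The fault lies in a conditional sensitivity analysis and in the claim made for it. The primary model and its outcome coding are not shown to be wrong. It should be fixed, but it does not undermine the main analysis.

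**What to change.** Keep the primary outcome coding. For the extreme-case analyses and for the count compared with 5%:

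- treat as missing every patient with a pre-operative value, no qualifying rise and one post-operative sample absent;
- hold at 0 every patient with no pre-operative value and both post-operative values below 15 ng/L.

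If the sponsor prefers to leave the analysis as it is, the claim of an absolute range should be removed and the result described as covering only patients coded missing under Appendix 1.

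As a minor tidy-up, add the two unlisted patterns to the missing category: pre-operative value present with both post-operative values absent, and pre-operative value absent with only one post-operative value.

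The cost is a few sentences of SAP text and a few lines of code. The reported range will usually be wider. The change is best made while contributors are still blind to the troponin results, as the SAP says they are.

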Appendix 1: Derived outcomes and variables

Variables

Revised cardiac risk index for pre-operative risk (RCRI)

RCRI is the sum of the following 6 components of the score:

- Elevated-risk surgery (Intraperitoneal; intrathoracic; suprainguinal vascular): 0=No; 1=Yes
- Ischaemic heart disease: 0=No: 1=Yes
- Heart failure: 0=No; 1=Yes
- Cerebrovascular disease (Prior TIA or stroke): 0=No; 1=Yes
- Pre-operative treatment with insulin (diabetes mellitus): 0=No; 1=Yes
- Pre-operative creatinine >2 mg/dL / 176.8 μmol/L: 0=No; 1=Yes

RCRI Score will range from 0-6. The total score will be set to missing if any items are missing.

Primary outcome

Myocardial injury within 48 hours of surgery

- Equal to 1 (Event) if:
 - Troponin-T ≥15 ng/L within 48 hours after surgery with a pre-operative value <15 ng/L or
 - Troponin-T increase ≥5 ng/L within 48 hours after surgery with a pre-operative value ≥15ng/L
- Equal to 0 (No Event) if:
 - o If the above definition of an 'event' is not satisfied and data collected on T-troponin pre-operative and post-operative day 1 or 2 is complete
- Equal to missing if:
 - o Data is missing for T-troponin pre-operative and post-operative day 1 & 2
 - Data is missing for T-troponin pre-operative and T-troponin post-operative day 1 & 2 is complete

Secondary outcomes

Peak level of Troponin-T measured within 48 hours of surgery

This is defined as the highest troponin-t value measured within 48 hours of surgery which is collected on post-op day 1 or day 2. If only one troponin-T value is available on post-op day 1 or day 2 then this will be used as the peak. If troponin-T data is missing for both post-operative day 1 & 2, then the outcome will be set to missing.

Infection within 30 days of surgery

This is defined as one or more of the following infections (more detail on the definition of each type of infection is available in the SPACE protocol):

- Superficial surgical site infection
- Deep surgical site infection
- Organ space surgical site infection
- Urinary tract infection
- Infection, source uncertain
- Laboratory confirmed blood stream infection

Equal to 1 if:

 At least one of the components of infection is listed as occurring (i.e. listed under Clavien-Dindo grade I-V)

Equal to 0 if:

• All of the components of postoperative infection are "None"

Missing if:

- All components are missing
- OR one or more of the components of postoperative infection is missing and all other components are "None"

Myocardial infarction within 30 days of surgery

Equal to 1 if:

Myocardial infarction is marked under Clavien-Dindo grade I-V

Equal to 0 if:

• Myocardial infarction is marked as "None"

Missing if:

Myocardial infarction is missing

Acute heart failure within 30 days of surgery

Note in the CRF acute heart failure is known as Cardiogenic pulmonary oedema Equal to 1 if:

• Cardiogenic pulmonary oedema is marked under Clavien-Dindo grade I-V

Equal to 0 if:

• Cardiogenic pulmonary oedema is marked as "None"

Missing if:

• Cardiogenic pulmonary oedema is missing

Stroke within 30 days of surgery

Equal to 1 if:

• Stroke is marked under Clavien-Dindo grade I-V

Equal to 0 if:

• Stroke is marked as "None"

Missing if:

Stroke is missing

Death within 30 days of surgery

Equal to 1 if:

- Patient status at 30-day follow-up is dead
- AND date of death is within 30 days of surgery

Equal to 0 if:

[figure not shown]
- Patient status at 30-day follow-up is alive
- OR patient status at 30-day follow-up is marked as 'dead' and date of death is not within 30 days of surgery

Missing if:

- Patient status at 30-day follow-up is missing
- Patient status at 30-day follow-up is marked as 'dead' and missing date of death

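### Patients coded as non-events on a single post-operative troponin are never counted as missing, so the extreme-case sensitivity analysis does not give the full range it claims

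*SAP*

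**What the plan says.** SAP section 3 bases myocardial injury on troponin "measured in blood samples collected immediately before the induction of anaesthesia, and then postoperative day 1 ± 6 hours and day 2 ± 6 hours after surgery". A qualifying value within 48 hours makes an event, so either post-operative sample can establish one.

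Appendix 1 (Primary outcome) then sets three states:

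- **Event:** the definition is met.
- **No event:** the definition is not met and "data collected on T-troponin pre-operative and post-operative day 1 or 2 is complete".
- **Missing:** either "Data is missing for T-troponin pre-operative and post-operative day 1 & 2", or "Data is missing for T-troponin pre-operative and T-troponin post-operative day 1 & 2 is complete".

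For peak troponin the same appendix says: "If only one troponin-T value is available on post-op day 1 or day 2 then this will be used as the peak". This supports reading the no-event rule as satisfied by one post-operative sample.

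The Sensitivity analysis paragraph in section 5 applies only if more than 5% of primary outcomes are missing. It sets missing outcomes to non-event in the continue group and event in the stop group, then reverses this. Of the two runs it says: "This will then give the absolute range of how much the results could change if the data were complete".

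**The concern.** One qualifying sample proves an event. One non-qualifying sample does not prove its absence, because the other day was not observed. A patient with a baseline and one negative post-operative sample therefore has incomplete data but is recorded as a non-event.

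Three things follow:

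- These patients do not count towards the 5% trigger. The only planned sensitivity analysis of the primary outcome may not run, even if many patients lack a sample.
- If it does run, they are held at 0 in both runs, so the reported range is narrower than the range compatible with complete data.
- No planned table shows how many there are. Table 4 would list them as patients with available data.

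What is at stake is mainly the credibility of the robustness statement, and only secondarily the primary estimate.

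**Working it through.** **Plan's own figure.** Inputs from section 4: 50% (stop) v 30% (continue), 5% significance, 90% power, 1:1 allocation; section 5 makes p-values two-sided. The pooled-variance formula for two proportions without continuity correction gives 124 per arm, or 248 in total, with power 90.0%. The stated sample size reproduces and is not in dispute.

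**Who is missing under the rule.** Both missing conditions, read literally, require the baseline to be absent. A patient with a baseline and one negative post-operative sample meets neither, and meets the no-event condition. The contribution to the trigger and to the width of the range is zero.

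**Illustrative size.** The SAP gives neither of the following, so both are assumed:

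- m, the share of patients with only one post-operative sample: 5% to 20%;
- s, the share of injuries that the one available sample shows: 75% unless stated.

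Formulas, with p the true rate in an arm and 130 randomised per arm:

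- observed rate = p × (1 − m(1 − s));
- share of the arm coded 0 on one sample = m × (1 − p × s);
- lower bound of the difference (stop minus continue) = observed difference minus that share in the continue arm;
- upper bound = observed difference plus that share in the stop arm.

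For m = 10%, s = 75%:

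- stop: 0.50 × 0.975 = 48.75%; continue: 0.30 × 0.975 = 29.25%; difference 19.5 points;
- coded 0 on one sample: stop 0.10 × (1 − 0.375) = 6.25%, or 8.1 of 130; continue 0.10 × (1 − 0.225) = 7.75%, or 10.1 of 130;
- share of all patients: (6.25% + 7.75%)/2 = 7.0%;
- bounds: 19.5 − 7.75 = 11.75 and 19.5 + 6.25 = 25.75 points.

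| m | Observed difference | Undetermined, all patients | Logical bounds | Power at 124 per arm |
|---|---|---|---|---|
| 5% | 19.75 points | 3.5% | 15.9 to 22.9 | 89.4% |
| 10% | 19.5 points | 7.0% | 11.8 to 25.8 | 88.7% |
| 20% | 19.0 points | 14.0% | 3.5 to 31.5 | 87.4% |

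If no patient is fully missing, the plan's own analysis would report 0% missing and no range in every row. At m = 20% with s = 60%, power is 85.6%.

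At m = 10%, an unadjusted pooled z-test with 130 per arm gives p of about 0.001 for the observed difference and about 0.056 at the lower bound.

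**Expected misses rather than bounds.** At m = 10%, s = 75%, the injuries actually missed number 130 × 0.10 × 0.50 × 0.25 = 1.6 in the stop arm and 130 × 0.10 × 0.30 × 0.25 = 1.0 in the continue arm.

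**Unequal loss with no true effect.** Take 40% in both arms and single-sample shares of 5% v 20%. The current coding produces a spurious difference of 0.40 × 0.15 × (1 − s), which is 0.6, 1.5 or 2.4 points for s = 90%, 75% or 60%. Setting single-sample negatives to missing while keeping single-sample positives gives an arm rate of p(1 − m(1 − s)) / (1 − m(1 − p × s)). At s = 75% this is 40.9% v 44.2%. The spurious difference is then 3.8, 3.3 or 2.6 points for the same values of s, in the opposite direction.

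**The case against.** The strongest defence is that the rule is deliberate. Section 5 sends the definition of a recorded outcome to Appendix 1, peak troponin follows the same convention, and using available samples keeps randomised patients in the analysis. Day 1 and day 2 are repeat readings of one biomarker, so a negative on one day is informative about the other. All of this stands as a reason to keep the primary coding. It does not rescue the range claim, because a partly observed patient held fixed in both runs cannot be covered by a range for complete data.

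Three stronger readings are tempting but not supported:

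- **That the primary result is seriously biased.** Under balanced loss the difference shrinks by only 0.5 points at 10% single-sample and 1.0 point at 20%. Nothing in the SAP indicates that sampling will differ between arms, and it expects missing primary outcome data to be minimal.
- **That the infection rule shows the correct coding.** Appendix 1 does make infection missing when "one or more of the components of postoperative infection is missing and all other components are" negative. Copying that rule into the primary model would keep single-sample events and discard single-sample non-events, which selects for events. In the null example above it is more biased than the current coding at each value of s.
- **That 11.8 to 25.8 points is the likely error.** It is reached only if every single-sample negative in one arm was injured and none in the other.

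Accepting a single value as the peak troponin is a reasonable convention for a secondary outcome. A both-samples check there would be a preference, not a correction.

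**Conclusion.** The point holds in a limited form. That these patients are coded 0, never counted as missing and never varied follows from the wording of Appendix 1 and the Sensitivity analysis paragraph alone. The claim made for the extreme-case range is therefore wrong if even one such patient exists.

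The size rests on two assumed quantities. With s = 75%, the undetermined share is below the 5% trigger at 5% single-sample (3.5%) and above it at 10% (7.0%). At 10% the unfavourable bound is enough to move a simple test across the 5% level, while the plan's analysis would show no movement. If nearly all patients have both samples, the effect is negligible. The change should be made, but the primary analysis does not fail without it.

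**What to change.** 1. Keep the primary coding: any qualifying sample is an event, and a single-sample negative stays 0 in the primary model.
2. Flag every patient coded 0 on one post-operative sample and report the number by arm in Table 4.
3. Count these patients towards the 5% trigger.
4. Vary them together with the fully missing patients in both extreme-case runs.
5. Add one run of the primary model limited to patients with both post-operative samples.

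If steps 2 to 5 are not wanted, remove the statement that the runs give the absolute range under complete data, and say that partly observed patients are not varied.

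The cost is SAP wording and a few lines of code, with no new data. The SAP's timing note says contributors are blinded to the primary outcome until samples are processed at the end of the trial, so at the date of this version the change could be made without knowledge of results. The downside is a wider, less favourable sensitivity range.
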